# 11.3.5.3. Assessment windows

As described in Section 11.3.5.1, the following assessment windows will be applied in order to be considered evaluable for the primary analysis, subjects must have at least one blood slide recorded during day 3 to day 5 or at day 7 (+/-1 day) and at day 28 (-1, +3 days).

Similarly, for the day 14 analyses, the assessment window will be day 14 (-1, +3 days); and for the day 42 analyses, the assessment window will be day 42 (-1, +3 days).

#### 11.3.5.4. Methods of Analysis

For the primary analysis, 95% C.I.'s will be unadjusted for covariates.

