## 7.5. Treatment Assignment

Subjects will be assigned to study treatment in accordance with the randomisation schedule. The randomisation schedule will utilise centre-based allocation.

The randomisation schedule will be generated by the Biomedical Data Sciences group at GSK, using Randall software. RAMOS will be used to allocate subjects to the treatment groups.

Once a randomisation number has been allocated to a subject, it cannot be re-assigned to any other subject at the site.

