#### 11.2.2. Sample Size Assumptions

A total of 650 evaluable patients in the CDA group and 325 evaluable patients in the artemether-lumefantrine group will provide **at least** 90% power to show non-inferiority of CDA to artemether-lumefantrine in terms of a one-sided hypothesis test with a 2.5% significance level for the primary endpoint of the parasitological cure rate at Day 28 (PCR corrected). This is based on using a 7% non-inferiority margin and a 2:1 allocation ratio, assuming 93% efficacy for CDA and 95% efficacy for artemether-lumefantrine amongst patients evaluable for the primary per-protocol population.

A 2:1 ratio has been chosen to preferentially collect information on the combination of CDA to artemether-lumefantrine, due to an interest in collecting additional safety data on the CDA arm.

In order to accommodate up to 30% loss of evaluable data due to missing data where patients are lost to follow-up, or have been lost to analysis due to retreatment for a new infection, it is planned that a total of 1395 patients will be enrolled (930 to CDA, 465 to artemether-lumefantrine).

At the time of sample size calculation for this study, the Day 28 PCR corrected Parasitological Cure Rate of artemether-lumefantrine was estimated to be 95% with values in the literature ranging between 93.5% to 97.5%. These parasitological cure rates have been observed in different trials run in different regions of the world at different times and in different populations.

It is expected that the efficacy rate for CDA will similarly be 95% (ie. a 0% treatment difference). However, due to the lack of data for CDA, a more conservative treatment difference is being used to calculate the sample size with 95% for artemether-lumefantrine and 93% for CDA (ie. a 2% treatment difference).

The impact on the power of the study due to deviations from assumed response rates is discussed in Section 11.2.3.

A single primary endpoint analysis has been defined for this study with a single treatment comparison. No adjustments for multiplicity are therefore required.

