#### 11.3.5.5. Subgroup analyses

No formal subgroup analyses are planned. However for investigative purposes 95% confidence intervals may be calculated within pooled centres, which will be pre-specified in the RAP. Summaries of the primary endpoint based on Age, Gender, and Ethnicity (if appropriate) will also be provided.

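### Allocation is by centre but the primary interval ignores centre; the crude interval stays valid, and stratifying it would be a small, cheap improvement

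*Protocol*

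**What the plan says.** - Section 7.5 (Treatment Assignment): "The randomisation schedule will utilise centre-based allocation". It does not say whether each centre has its own blocked list.
- Section 11.3.5.4 (Methods of Analysis): "For the primary analysis, 95% C.I.'s will be unadjusted for covariates". No reason is given.
- Section 11.3.5.5 (Subgroup analyses): "for investigative purposes 95% confidence intervals may be calculated within pooled centres, which will be pre-specified in the RAP". These are separate intervals within groups of centres, and optional. They are not an overall interval adjusted for centre.
- Section 11.2.2 sizes the trial as a plain comparison of two proportions: "A total of 650 evaluable patients in the CDA group and 325 evaluable patients in the artemether-lumefantrine group", with a "one-sided hypothesis test with a 2.5% significance level", "using a 7% non-inferiority margin and a 2:1 allocation ratio", and assumed cure rates of 93% and 95%.
- Sections 11.3.5.1 and 11.3.5.2 remove PCR-confirmed new infections from the efficacy analyses, in the ITT population as well as the per-protocol one. Section 11.2.2 allows for up to 30% loss of evaluable data.

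**The concern.** A factor that governs allocation should normally appear in the main analysis. When arms are balanced within centre, differences between centres do not contribute to the sampling error of the treatment difference. A crude two-proportion standard error still counts them, so the interval is wider than it needs to be.

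A second issue is specific to this trial. Randomisation can balance centres at entry, but the primary comparison uses those who remain after losses and after re-infections are removed. Re-infection depends on local transmission. If removal depends on both centre and arm, the centre mix can differ between arms in the analysed set, and a crude difference carries that imbalance. The ITT analysis removes re-infections too, so it does not repair this.

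At stake are a little precision in the single confirmatory interval and some protection against imbalance after randomisation.

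**Working it through.** **Inputs.** From Section 11.2.2: 650 and 325 evaluable, cure 93% (CDA) and 95% (artemether-lumefantrine), margin 7 points, one-sided 2.5%. Assumed, because the protocol does not give it: a between-centre SD *s* of the cure rate, taken as equal in both arms.

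**Step 1: the plan's own figure.** With unpooled variance,

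SE = √(0.93×0.07/650 + 0.95×0.05/325) = √(0.00010015 + 0.00014615) = 1.569 points.

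Power = Φ((7 − 2)/1.569 − 1.96) = Φ(1.226) = 89.0%.

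With the Table 1 counts (605/650 and 309/325) the same formula gives 89.4%, against 90.6% in the table. The stated power is reproduced to within about 1 point, so the crude analysis matches the sample size basis.

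**Step 2: remove the between-centre part.** The average within-centre variance of a binary outcome is p(1−p) − s². Hence

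SE(stratified) = √((0.0651 − s²)/650 + (0.0475 − s²)/325).

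For s = 4 points: √(0.0635/650 + 0.0459/325) = 1.546 points, a ratio of 0.985 to the crude SE. Power = Φ(5/1.546 − 1.96) = 89.9%. The equivalent number of patients is 975 × (1/0.9849² − 1) ≈ 30.

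| s (points) | SE reduction | CI half-width (points) | Power | Equivalent extra evaluable |
|---|---|---|---|---|
| 0 | 0 | 3.08 | 89.0% | 0 |
| 1 | 0.1% | 3.07 | 89.0% | 2 |
| 2 | 0.4% | 3.07 | 89.2% | 7 |
| 3 | 0.9% | 3.05 | 89.5% | 17 |
| 4 | 1.5% | 3.03 | 89.9% | 30 |
| 7 | 4.7% | 2.93 | 91.7% | 99 |

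The power column is compared with the planning figure of 89.0%. If allocation really is balanced within centre, the crude interval also benefits: its power is Φ((5 − 1.96×1.569)/SE(stratified)), which is 89.3% at s = 4. The gain from changing the interval alone is then about 0.5 point, not 0.9.

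**Step 3: is the spread plausible?** The only range given for one drug is 93.5% to 97.5% for artemether-lumefantrine across trials and regions (Section 11.2.2). A uniform spread over it has SD 4/√12 ≈ 1.2 points. The 86% to 100% range in Section 11.2.1 mixes drugs and studies. Spread uniformly it gives 14/√12 ≈ 4.0 points, a generous upper bound. An SD of 7 points would need, for example, half the centres at 86% and half at 100%.

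**Step 4: simulation.** With 40,000 trials per scenario, 6 to 25 centres of equal or skewed size and SD 0 to 2.5 points, the Mantel-Haenszel difference with Sato variance was compared with the crude interval. Width shrank by 0 to 0.6%, power changed by −0.2 to +0.5 point, and one-sided type I error was 2.0% to 2.4% for both.

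**Step 5: exclusion imbalance, illustration only.** All rates here are assumed. Half the patients are at high-transmission sites, where 30% of CDA and 15% of comparator patients are excluded; elsewhere 5% of each arm are. Cure is 90% at high-transmission sites and 97% elsewhere, identical between arms.

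- High-transmission share, CDA: 0.35/(0.35 + 0.475) = 42.4%.
- High-transmission share, comparator: 0.425/(0.425 + 0.475) = 47.2%.
- Crude difference: 7 × (0.472 − 0.424) ≈ +0.34 point for CDA, when the truth is zero.

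Stratifying by site type removes it. Other inputs would change its size and could change its sign.

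**The case against.** The strongest reply is that nothing is broken. The unadjusted interval is pre-specified, matches the calculation that sized the trial, and errs on the conservative side where precision is concerned. That stands.

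A reader might infer that the mismatch with allocation makes the primary interval invalid, or that a substantial number of patients is wasted. The documents support neither. Type I error stays at or below the nominal 2.5% in the simulations, and the equivalent of some 80 or more patients appears only when the between-centre SD approaches 7 points, which nothing in the protocol suggests.

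A reader might also infer that exclusions bias the result in favour of CDA. The protocol gives no exclusion rates by centre and arm. The 30% is an overall planning allowance, and the direction in the illustration follows from the rates chosen.

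It can also be said that Section 11.3.5.7 leaves the list of sensitivity analyses open, so the RAP could add a stratified interval. It could, but that would not alter the primary method fixed in Section 11.3.5.4.

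Finally, stratification is not entirely free. The assumed rates imply about 0.07×650 + 0.05×325 ≈ 62 failures in all, so some centres may have few or none and would have to be pooled by rule.

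**Conclusion.** The point holds as a modest improvement. The protocol specifies a primary interval that leaves out the factor used for allocation, without giving a reason. For an assumed between-centre SD of 1 to 4 points, stratification narrows the SE by about 0.1% to 1.5% and adds 0 to about 0.9 point of power against the planning figure, or about 0.5 point at most if allocation is already balanced within centre. With equal centres the gain is nil.

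Protection against centre imbalance after exclusions is a sound further reason, but its size cannot be established from the protocol. These figures rest on the assumed spread, taken as equal in both arms. That the crude interval is too wide also depends on reading Section 7.5 as balance within centre. The primary conclusion is not threatened.

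**What to change.** In Section 11.3.5.4, define the primary 95% interval as a centre-stratified risk difference, CDA minus artemether-lumefantrine, using Mantel-Haenszel weights with the Sato variance or a stratified Miettinen-Nurminen interval. Take as strata the pooled centres that Section 11.3.5.5 already assigns to the RAP, and fix there, before unblinding, the rule for pooling small or zero-failure centres. Keep the -7% criterion and the sample size, and report the unadjusted interval as a sensitivity analysis.

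The cost is one sentence, one standard procedure and the pooling rule. No additional patients or data are needed.

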#### 11.3.5.5. Subgroup analyses

No formal subgroup analyses are planned. However for investigative purposes 95% confidence intervals may be calculated within pooled centres, which will be pre-specified in the RAP. Summaries of the primary endpoint based on Age, Gender, and Ethnicity (if appropriate) will also be provided.

#### 11.3.5.6. Deviations from the Planned Analyses

Any deviations from the analyses planned as part of this protocol will be documented in the Reporting and Analysis Plan (RAP), prior to unblinding.

# 11.3.5.7. Efficacy Analyses

The primary analysis is the Per Protocol analysis of the Parasitolgical Cure Rate (PCR-corrected) at Day 28.

A key supportive analysis will be the Intent-to-Treat analysis of the Parasitological Cure Rate (PCR-corrected) at Day 28, with missing data imputed as treatment failure

Additional sensitivity analyses of the primary endpoint will be performed to assess the robustness of the primary analysis to modifications in assumptions and methods. Analyses such as the following will be performed:

- Intent-to-Treat analysis of the Parasitological Cure Rate (PCR-corrected) at Day 28, with missing data excluded.
- Per Protocol analysis of the Parasitological Cure Rate (without PCR correction) at Day 28.

Secondary Analyses will include:

- Parasitological cure rate of CDA vs artemether-lumefantrine at day 14 (PCR corrected).
- Parasitological cure rate of CDA vs artemether-lumefantrine at day 42 (PCR corrected).
- Adequate Clinical and Parasitological Response rate (ACPR [World Health Organisation, 2003]) at day 14, 28 and 42 (all PCR corrected).
- Asexual parasite densities over time for CDA vs. artemether-lumefantrine.
- PCT of CDA vs artemether-lumefantrine.

- Gametocyte density over time of CDA vs artemether-lumefantrine.
- FCT of CDA vs artemether-lumefantrine.

Details of theses analyses will be documented in the Reporting and Analysis Plan (RAP).

#### 11.3.5.8. Safety Analyses

All safety reporting will be based on the intent-to-treat population.

#### 11.3.5.8.1. Extent of Exposure

Subjects will be dosed on Day 0, 1 and 2 of the study. The extent of exposure will be the number of doses of study medication administered to the subject (regardless of whether vomited).

The duration of exposure to study medication will be defined as date of last dose of active study medication – date of first dose of study medication + 1. Extent and duration of exposure will be summarised using a frequency distribution for number of doses and number of days.

#### 11.3.5.8.2. Adverse Events

Adverse Event (AE) reporting will be performed using the MedDRA (Medical Dictionaries for Regulatory Activities) coding system. Each AE coded using the MedDRA system can be associated with more than one system organ class (SOC). However, for reporting purposes, an AE will be associated with the primary system organ class only.

Counting of adverse events will be based on the number of subjects – not the number of AEs. For example, if a subject reports the same AE on three occasions within a time interval, that AE will only be counted once. Subjects reporting more than one AE in a system organ class will only be counted once in the system organ class total.

All treatment-emergent AE's (i.e. with onset time on or after that of first dose), will be listed and a summary table will be prepared showing the incidence of all recorded AEs by treatment group. However, all other AE tabulations will be produced excluding occurrences of PCR-confirmed P. fulciparum recrudescence. Such events will be classified as treatment failures for the purposes of efficacy analyses but will not be considered AEs for the purposes of comparing the AE profiles between the two treatment groups. Occurrences of new malarial infection, as confirmed by PCR will remain as adverse events and will be reported in all the AE outputs. The following summary tables will be produced for all AEs except those confirmed as recrudescences:

AE's by preferred term and SOC, AE's in descending order of frequency, AE's by maximum severity (mild, moderate or severe).

AE's considered by the investigator to have a reasonable possibility of being related to treatment ('drug-related' AEs) will be summarised by preferred term and SOC.

AE's leading to premature withdrawal from treatment will be summarised by preferred term and SOC.

AE's leading to premature withdrawal from study will be summarised by preferred term and SOC.

AE's that are considered to be haematologically-related will be identified for reporting by clinical review of blinded AE data. Haematological AE's will be summarised by preferred term and SOC.

Serious adverse events will be summarised by preferred term and SOC.

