## 10.2. Definition of a SAE

A serious adverse event is any untoward medical occurrence that, at any dose:

- a. Results in death.
- b. Is life-threatening.

NOTE: The term 'life-threatening' in the definition of 'serious' refers to an event in which the subject was at risk of death at the time of the event. It does not refer to an event, which hypothetically might have caused death, if it were more severe.

c. Requires hospitalization or prolongation of existing hospitalization.

NOTE: In general, hospitalization signifies that the subject has been detained (usually involving at least an overnight stay) at the hospital or emergency ward for observation and/or treatment that would not have been appropriate in the physician's office or out-patient setting. Complications that occur during hospitalization are AEs. If a complication prolongs hospitalization or fulfils any other serious criteria, the event is serious. When in doubt as to whether "hospitalization" occurred or was necessary, the AE should be considered serious.

Hospitalization for elective treatment of a pre-existing condition that did not worsen from baseline is not considered an AE.

d. Results in disability/incapacity, or

NOTE: The term disability means a substantial disruption of a person's ability to conduct normal life functions. This definition is not intended to include experiences of relatively minor medical significance such as uncomplicated headache, nausea, vomiting, diarrhea, influenza, and accidental trauma (e.g. sprained ankle) which may

interfere or prevent everyday life functions but do not constitute a substantial disruption.

- e. Is a congenital anomaly/birth defect.
- f. Medical or scientific judgement should be exercised in deciding whether reporting is appropriate in other situations, such as important medical events that may not be immediately life-threatening or result in death or hospitalization but may jeopardize the subject or may require medical or surgical intervention to prevent one of the other outcomes listed in the above definition. These should also be considered serious. Examples of such events are invasive or malignant cancers, intensive treatment in an emergency room or at home for allergic bronchospasm, blood dyscrasias or convulsions that do not result in hospitalization, or development of drug dependency or drug abuse.

Additionally, the following protocol specific events will be reported as SAEs:

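### PCR-confirmed recrudescences are left out of the SAE and maximum-severity tables even when the event is serious or fatal

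*Protocol*

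**What the plan says.** All of the reporting rules are in Protocol section 11.3.5.8.2. Treatment-emergent AEs will be "listed and a summary table will be prepared showing the incidence of all recorded AEs by treatment group". That listing and that one table are the only outputs that retain recrudescences. The next sentence reads: "However, all other AE tabulations will be produced excluding occurrences of PCR-confirmed P. fulciparum recrudescence". The reason given is that a recrudescence counts as a treatment failure for efficacy and so should not also count when AE profiles are compared between arms.

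New infections are handled the other way: "Occurrences of new malarial infection, as confirmed by PCR will remain as adverse events and will be reported in all the AE outputs".

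The tables are then introduced with "The following summary tables will be produced for all AEs except those confirmed as recrudescences". They cover preferred term and SOC, frequency, maximum severity, drug-related events, withdrawal from treatment, withdrawal from study, haematological events and, last, serious events: "Serious adverse events will be summarised by preferred term and SOC". None carries an exception for serious or fatal cases.

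Section 10.2 opens its definition with "A serious adverse event is any untoward medical occurrence that, at any dose" and lists death, threat to life and hospitalisation among the criteria. It does not exempt recrudescence.

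**The concern.** Keeping efficacy failures out of routine AE frequency tables is a reasonable choice, because otherwise the tables would largely repeat the cure-rate result. That reasoning does not carry over to the SAE table, whose job is to show how often serious harm occurred in each arm, whatever the cause.

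Under the rule as written, whether a serious malaria episode after Day 7 appears in that table depends on a genotyping result. A match to the baseline parasite removes it; a mismatch or an inconclusive result leaves it in. The cure rate does not make up for this, because it scores an asymptomatic positive slide and a fatal recrudescence alike. Reporting the safety and tolerability of CDA is a stated secondary objective (section 2.2), and the by-arm SAE table is a central summary for it.

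**Working it through.** No figure in the protocol is in dispute, so the check is mainly a comparison of sections.

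**Does the exclusion reach the SAE table?**
- The general sentence in section 11.3.5.8.2 covers every AE tabulation other than the all-AE table.
- The lead-in to the list of tables repeats the exclusion.
- The SAE table is the last item after that lead-in and has no carve-out. The maximum-severity table is in the first group.
- The Amendment 04 summary describes the intent in the same terms, so this does not look like a drafting slip.

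**Can a recrudescence be an SAE?**
- Section 10.2: yes, if it meets any seriousness criterion.
- Section 6.3.4 foresees such cases, since severe malaria or danger signs after Day 3 with parasitaemia is a form of late clinical failure.
- Section 11.3.5.8.2 presupposes that recrudescences are recorded as AEs, because it keeps them in the all-AE table.

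**What happens to otherwise identical serious episodes?**

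| Episode | In SAE table? | Basis |
|---|---|---|
| PCR-confirmed recrudescence | No | 11.3.5.8.2 |
| PCR-confirmed new infection | Yes | 11.3.5.8.2 |
| Inconclusive PCR (an efficacy failure under 6.3.3) | Yes | not a confirmed recrudescence |
| Severe malaria before Day 7 | Yes | PCR classification starts at Day 7 (6.3.2) |

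**Effect on the withdrawal tables.** The list also includes "AE's leading to premature withdrawal from treatment will be summarised by preferred term and SOC" and "AE's leading to premature withdrawal from study will be summarised by preferred term and SOC". Dosing is on Days 0 to 2 (section 11.3.5.8.1) and PCR classification starts at Day 7, so the first of these should hardly change. Treatment failures receive rescue medication and stay in safety follow-up to Day 42 (section 6.3.4), so the second should change little.

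**Scale.** Inputs are the evaluable numbers in section 11.2.2 (650 and 325) and the cure counts in section 11.2.3, Table 1 (605 of 650 and 309 of 325), which correspond to the assumed 93% and 95%.
- CDA failures: 650 − 605 = 45, and 45/650 = 6.9%.
- Artemether-lumefantrine failures: 325 − 309 = 16, and 16/325 = 4.9%.

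Under these rates, recrudescences to Day 28 among evaluable subjects could not exceed these counts, because inconclusive PCR is also scored as failure. Recrudescences between Day 28 and Day 42 would add to them. The protocol gives no proportion of recrudescences that are serious, so the calculation stops here.

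**The case against.** The strongest reply is that nothing is concealed. The events stay in the listing and in a by-arm table, every SAE goes to the sponsor within 24 hours (section 10.4.1), and the IDMC reviews efficacy and safety together (section 11.3.4). The secondary ACPR classification separates late clinical failure from late parasitological failure, so clinical and afebrile failures are not merged everywhere. The different handling of new infections also has a logic: they are excluded from the efficacy analysis and so counted as AEs, while recrudescences are counted in efficacy. Separately recorded complications, such as the haemoglobin falls and transfusions that section 10.2 makes protocol-specific SAEs, appear to stay in, because only the recrudescence itself is removed.

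Most of this stands, and it limits the point. It does not remove it. The all-AE table is not said to show seriousness, late clinical failure also includes febrile parasitaemia that is not serious, and the one-domain logic does not justify an SAE table that omits SAEs.

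A reader might go further and infer that serious harm is hidden in the arm with more failures, that the SAE comparison is materially biased, or that a definite number of SAEs will be missing. The documents support none of these. Section 11.2.2 expects 95% cure in both arms and uses 93% for CDA only as a conservative planning value, so a difference in recrudescence is not the expected case. Any serious fraction would be an outside assumption. If every failure above were a recrudescence and 5% to 10% were serious in both arms (an assumed range with no basis in the protocol), the difference in omitted SAE rates would be (6.9% − 4.9%) × 0.05 to 0.10, or 0.1 to 0.2 percentage points.

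**Conclusion.** The point holds as a defect in a reporting rule that the protocol itself fixes, so it is not a detail left to the analysis plan. A recrudescence that is an SAE under section 10.2 is absent from the by-arm SAE and maximum-severity summaries, while new infections and inconclusive-PCR cases of the same seriousness are present. This rests on the natural reading of section 11.3.5.8.2 and needs no numerical assumption.

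The size is not known. The 45 of 650 and 16 of 325 are planning-rate failures to Day 28 in evaluable subjects and are not SAE counts. The effect on the withdrawal tables is likely small. The point merits correction because a single omitted death would make the SAE table incomplete; no large distortion has been shown.

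**What to change.** In section 11.3.5.8.2, limit the exclusion of PCR-confirmed recrudescence to the routine AE frequency tables. State that the SAE table (deaths included) and the maximum-severity table include all events whatever the PCR result, with recrudescence on its own line so that each can be read with and without it.

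The cost is a change of wording and one flag in tables already planned. No study procedure or efficacy analysis changes, and the sponsor's preferred view without recrudescence stays available. The SAE rate may look slightly less favourable.
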